12.5 Expedited Reporting of Related Unexpected SAEs

If an SAE is identified as being related and unexpected by the Chief Investigator it will be reported by ICR-CTSU to the main REC, the Sponsor and all other interested parties within 15 days of being notified of the event.

The Principal Investigators at all actively recruiting sites will be informed of any related unexpected SAEs occurring within the trial at appropriate intervals.

The collaborative group in each participating country will report related unexpected SAEs as per their local requirements to IECs and local investigators.

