5.2 Source of Participants

Participants will be recruited from approximately 20 sites in the UK plus additional sites from participating countries within the EORTC network. Potential participants will be identified in oncology clinics and discussed at local Multi-Disciplinary Team (MDT) meetings.

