10.3 Post-treatment Follow-up

All patients will be assessed 8 weeks post randomisation and then subsequently at 3 monthly intervals (from 8 week assessment date) in line with routine care until disease progression is confirmed. The following assessments will be performed at each visit:

- Karnofsky Index and ECOG performance status
- Toxicity assessment including MRC dyspnoea score
- Post treatment QoL questionnaire (at 8 weeks post randomisation and first subsequent follow-up visit).
- Full blood count, urea, electrolytes and liver function tests (first 3 month visit only, not required thereafter)
- Tumour imaging assessment (imaging requirements at follow up visits will be determined by lesion location as identified at trial entry. The same imaging modality used at baseline should be used for subsequent follow-up assessments. Consideration should be given for repeat CT contrast/MRI brain as required)
- Current medication / treatment

Research blood samples will be taken at 8 weeks, 5 months and 8 months post-randomisation and upon progression (for patients randomised to receive SBRT an additional sample will be taken after delivery of the first fraction of SBRT).

Repeat SBRT – Only those patients allocated SBRT treatment at randomisation should be offered repeat SBRT treatment upon development of new OPD lesions or progression of existing extracranial lesions not progressing at trial entry, where the total number of progressing lesions at any one point remains ≤ 5 . Suitability of new OPD lesions for further SBRT will be based on the same criteria as at trial entry (visible, imaging defined targets suitable for SBRT, \leq 7cm). Where multiple lesions are treated over the course of the trial, composite dose volume data must be assessed and all normal tissue dose constraints need to be met by the composite plan. Particular caution is required where isodose lines overlap serial organs. Any previous radiotherapy before trial entry should also be taken into account. 50% isodose lines for plans to individual lesions should not overlap. A maximum of 5 thoracic lesions, 3 abdominal and 3 pelvic lesions can be considered for SBRT with composite planning confirming all normal tissue dose constraints are met.

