11.6 SBRT Scheduling

Initial SBRT treatment should commence within 4 weeks of randomisation, subsequent rounds of treatment (as necessary upon further progression not meeting the primary endpoint) should be scheduled as per local guidelines. SBRT can start on any day of the week and will be delivered as per the table above and detailed in the HALT Radiotherapy Planning and Delivery Guidelines document, where the maximum number of days treatment should be delivered being dependent on the dose fractionation schedule being used. If the maximum duration for the SBRT course is exceeded due to patient or radiotherapy service delivery factors please contact the HALT trial manager ([contact]).

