15 RESEARCH GOVERNANCE

15.1 Sponsor Responsibilities

The Sponsor of this clinical trial is the Institute of Cancer Research (ICR). The Sponsor is responsible for securing the arrangements to initiate, manage and finance the trial.

A coordinating group in each participating (non-UK) country will be delegated responsibility for trial initiation and conduct in that country on behalf of the Sponsor, as defined in an agreement between the Sponsor and the coordinating group.

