- Rectal Haemorrhage
- Haematuria
- Urinary frequency
- Urinary incontinence
- Urinary retention
- Urinary urgency

General

- Fever
- Fatigue
- Myelitis

Dermatology/Skin

- Dermatitis
- Hair loss (to treatment area)

Related to fiducial marker insertion

- Bleeding
- Sepsis (urinary and systemic)
- Pneumothorax

A7. Non-UK safety reporting requirements

The site Principal Investigator or designee is responsible for reporting SAEs to the ICR-CTSU as per the protocol.

[figure not shown]
The EORTC will report related unexpected SAEs as per national requirements to IECs and local investigators.

Further Sponsor safety reporting notification requirements will be agreed in the international site agreements.

HALT Protocol

ICR-CTSU

A8. Translational study collection (6 sampling points per patient)

GL DNA = Germ Line DNA (collected in EDTA tube)

cfDNA = circulating free tumour DNA (Streck tube)

RNA = RNA for analysis of T cell Repertoire from peripheral blood (1 x Tempus[™] blood RNA tube – 3ml blood draw)

FFPE Research Block: When available additional cores from biopsy of oligoprogressive lesions should be placed in a separate pot for fixation in FFPE at baseline and at the time of progression if biopsy was clinically indicated. Clinical diagnostic requirements take precedence.

HALT Protocol

ICR-CTSU

A9. GLOSSARY

AE	Adverse Event
ALT	Alanine Aminotransferase
ANC	Absolute Neutrophil Count
AST	Aspartate Aminotransferase
AUC	Area Under Curve
CI	Chief Investigator
CIS	Carcinoma In Situ
CRF	Case Report Form
DCF	Data Capture Form
DFS	Disease Free Survival
eCRF	Electronic Case Report Form
ECOG	Eastern Cooperative Oncology Group
EORTC	European Organisation for Research and Treatment of Cancer
FBC	Full Blood Count
G-CSF	Growth Colony-Stimulating Factors
GFR	Glomerular Filtration Rate
HR	Hazard Ratio
IB	Investigator's Brochure
ICR	The Institute Of Cancer Research
IDMC	Independent Data Monitoring Committee
LFT	Liver Function Test
MDT	Multi-disciplinary team
MRC	Medical Research Council
NCI CTCAE	National Cancer Institute Common Terminology Criteria for Adverse Events
OAR	Organs At Risk
PI	Principal Investigator
PIS	Patient Information Sheet
QoL	Quality of Life
R&D	Research and Development
RCT	Randomised controlled trial
RTTQA	NCRI Radiotherapy Trials Quality Assurance
SAE	Serious Adverse Event
SAR	Serious Adverse Reaction
SBRT	Stereotactic Body Radiotherapy
SMPC	Summary of Product Characteristics
SUSAR	Suspected Unexpected Serious Adverse Reaction

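### For UK sites, the explicit commitment in section 12.5 to tell Principal Investigators of related unexpected SAEs covers only sites still recruiting, although first or repeat SBRT can be given after a site has stopped.

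*Protocol*

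**What the plan says.** Protocol section 12.5 sets out three routes for an SAE judged related and unexpected.

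- **Expedited report.** For such an event, "it will be reported by ICR-CTSU to the main REC, the Sponsor and all other interested parties within 15 days of being notified". The interested parties are not defined here, nor in section 12.4 where they also appear.
- **Notice to site investigators.** "The Principal Investigators at all actively recruiting sites will be informed of any related unexpected SAEs occurring within the trial at appropriate intervals". No time limit is given.
- **Country route.** "The collaborative group in each participating country will report related unexpected SAEs as per their local requirements to IECs and local investigators". Appendix A7, on non-UK reporting, says the same of the EORTC: "The EORTC will report related unexpected SAEs as per national requirements to IECs and local investigators".

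Section 15.1 places the country groups outside the UK: "A coordinating group in each participating (non-UK) country will be delegated responsibility for trial initiation and conduct in that country". Section 5.2 shows how much of the trial is in the UK: "Participants will be recruited from approximately 20 sites in the UK plus additional sites from participating countries within the EORTC network".

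On exposure, section 9 asks for SBRT to start within 4 weeks of randomisation. Section 10.3 says "Only those patients allocated SBRT treatment at randomisation should be offered repeat SBRT treatment upon development of new OPD lesions", and section 11.6 adds that "subsequent rounds of treatment (as necessary upon further progression not meeting the primary endpoint) should be scheduled as per local guidelines". None of these depends on whether the site is still recruiting.

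**The concern.** Recruitment status is a poor marker of who needs the information. An event of this kind is new evidence of SBRT risk, because by definition it is not on the expected list in Appendix A6. The investigator who needs it is the one about to give SBRT, whether or not the site still enrols.

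The protocol itself treats the risk as continuing and not fully known. Section 11.1 acknowledges uncertainty about the safety of TKI given alongside SBRT. Sections 12.1 and 12.3 collect SAEs for 90 days after a repeat course and severe radiotherapy events up to a year. The trial therefore expects to learn of harms after sites have stopped recruiting. Read literally, the sentence addressed to site investigators has no recipients once accrual ends. For UK sites no other sentence names them.

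**Working it through.** **Step 1: who is named as a recipient.**

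| Route | Recipients | Recruitment limit? | Covers a UK site that has stopped recruiting? |
|---|---|---|---|
| 12.5, expedited report | Main REC, Sponsor, other interested parties (undefined) | No | Neither guaranteed nor excluded |
| 12.5, notice to Principal Investigators | Actively recruiting sites | Yes | No |
| 12.5 and Appendix A7, country group or EORTC | Ethics committees and local investigators | No | Apparently not; the groups are non-UK (15.1) |
| 12.7, annual report | Main REC, Sponsor, country groups | No | No; site investigators are not listed |
| 14.3, IDMC release | TMG through the TSC, and participants if appropriate | No | Discretionary; not a notice to each investigator |

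The third row assumes that the collaborative groups of section 12.5 are the coordinating groups of section 15.1. The title of Appendix A7 supports that reading.

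**Step 2: can SBRT follow the end of recruitment at a site?** Yes, in two ways. A patient randomised on a site's last day has up to 4 weeks before the first fraction (section 9). An SBRT-arm patient who has not met the primary endpoint may be offered another course (sections 10.3 and 11.6). Section 13.1 plans at least 6 months of follow-up after accrual.

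**Step 3: scale, as illustration only.** The protocol gives no figure here to reproduce.

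Inputs:
- SBRT arm: 73 patients (section 5.1).
- Accrual: 36 months, in six-month blocks of 5, 10, 15, 20, 25 and 25% (section 13.1).
- Median PFS with SBRT: 6 months (section 13.1).
- Exponential PFS: my assumption.

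With a 6-month median, the mean probability of being event-free at month 36 for patients entered evenly over the last block is (1 − 0.5)/ln 2 = 0.7213. It halves for each earlier block.

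| Block (latest first) | Share of accrual | Mean event-free probability | Product |
|---|---|---|---|
| Months 30–36 | 0.25 | 0.7213 | 0.1803 |
| Months 24–30 | 0.25 | 0.3607 | 0.0902 |
| Months 18–24 | 0.20 | 0.1803 | 0.0361 |
| Months 12–18 | 0.15 | 0.0902 | 0.0135 |
| Months 6–12 | 0.10 | 0.0451 | 0.0045 |
| Months 0–6 | 0.05 | 0.0225 | 0.0011 |
| Sum | | | 0.3257 |

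- Event-free at month 36: 73 × 0.3257 = 23.8, about 24 of 73 (33%).
- Event-free at month 42, one median later: 23.8 / 2 = 11.9.
- Randomised to SBRT in the last 4 weeks: 73 × 0.25 × (28/30.4375)/6 = 2.8, about 3.

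**Step 4: what these numbers bound.** Being event-free is necessary for repeat SBRT but not sufficient. Section 10.3 also requires suitable new or newly progressing lesions, and normally more than 3 months since the last SBRT. Of the 24, those randomised in the last 3 months number 73 × 0.25 × 0.5 × 0.845 = 7.7, where 0.845 = (1 − 2^(−0.5))/(0.5 × ln 2). About 8 would therefore normally not qualify at the moment of closure. The figure of 3 is also an upper limit, since it supposes that nobody starts before week 4.

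**The case against.** A reader might infer that these SAEs go only to recruiting sites, that other sites are not told, or that the rule withholds the information. The documents support none of these. Non-UK investigators have a route with no recruitment limit. The sentence on Principal Investigators does not forbid wider notice, and a UK investigator about to give SBRT could be counted among the interested parties.

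There are also central safeguards. Section 11.7 requires prospective review before any repeat SBRT. Under section 13.4 the IDMC reviews emerging safety data, and the grade 4/5 stopping consideration includes repeat courses. These weaken any claim that patients at closed sites are unprotected. They do not replace a notice: the review in 11.7 covers outlining and planning compliance, and release by the IDMC is at its discretion. Since section 12.5 gives investigators their own sentence, with narrower scope and looser timing than the 15-day report, the natural reading is that this sentence is the one meant to govern them.

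A reader might also take the 24 patients as those due repeat SBRT. They are not. The protocol states no repeat-SBRT rate, no frequency of related unexpected SAEs and no UK share. Nor is closure of every site at month 36 certain: Appendix A1 allows accrual to run past the phase II target while funding is sought, and into phase III if it is granted. Finally, the concern does not rest on re-treating irradiated lesions, which section 10.3 does not permit.

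**Conclusion.** The point holds for UK sites. The only stated commitment to inform their Principal Investigators uses recruitment status, while SBRT can continue after recruitment stops. What is missing is an explicit guarantee of notice; the protocol contains no prohibition, and practice may already be wider than the text.

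If accrual closes at 36 months and PFS is exponential with a 6-month median, the pool of possible repeat-SBRT candidates at closure is at most about 24 of 73 across all sites, with at most about 3 awaiting first SBRT. A UK site that closes earlier would meet the same gap before month 36. This is a matter of safety communication. It affects no endpoint or analysis, but it is worth correcting because the remedy is so small.

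**What to change.** In section 12.5, change the recipients of the investigator notice from actively recruiting sites to all sites with any participant still in trial treatment or follow-up. This brings the UK route into line with the non-UK route, which has no recruitment limit. Defining the other interested parties in sections 12.4 and 12.5 would remove the remaining ambiguity.

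The cost is a few words in the protocol, a longer distribution list and a few more notifications to sites that no longer recruit. No clinical rule or statistical analysis changes.

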12.6 Follow up of Serious Adverse Events

SAEs should be followed up until clinical recovery is complete or until disease has stabilised. SAE outcomes should be reported to ICR-CTSU using the relevant section of the SAE form as soon as the Principal Investigator or designee becomes aware of the outcome.

12.7 Annual Safety Reporting

[figure not shown]
An annual progress report will be provided to the main REC by ICR-CTSU and copied to the Sponsor and the collaborative group in each participating country at the end of the reporting year. This will include data about related unexpected SAEs and whether any safety concerns have arisen during the reporting period.

12.8 Reporting Pregnancies

If any trial participant becomes pregnant while receiving trial treatment or up to 90 days after receiving trial treatment, this should be reported to ICR-CTSU using the pregnancy reporting form. Participants who become pregnant should discontinue from trial treatment immediately. Pregnancies should be followed up until conclusion and all follow-up information should be reported to ICR-CTSU.

If the outcome of the pregnancy meets the definition of serious (i.e. congenital abnormality) this should be reported to ICR-CTSU following the serious adverse event reporting procedures described above.

ICR-CTSU

NB. All SAEs should continue to be followed up as specified above

13 STATISTICAL CONSIDERATIONS

13.1 Statistical Design and Sample Size Justification

HALT is a randomised, multi-centre, phase II/III study with planned international participation. The integrated phase II/III trial incorporates a transition to full phase III dependent on feasibility data obtained during the phase II trial. This design offers the most efficient use of time and resource compared to a standalone phase II trial followed by a separate phase III trial and allows maximum return of information in a relatively short timeframe. Progression to the phase III trial will be dependent on emerging feasibility data from the phase II trial including recruitment rates; safety and extent of opportunities for international participation (see section 11.5). With the development of novel actionable mutations and TKIs continuing to emerge both the phase II and III components of the study have proposed adaptive aspects to allow inclusion of additional patient groups with OPD on any other targeted treatments as they are introduced into routine practice.

Limited data is available on oligo-progression in patients with NSCLC, however a median time from radiological oligo-progression to widespread progression when continuing on a TKI alone (as per the control group) of approximately 3 months was estimated following a survey of U.K. oncologists and clinical members of the trial team. Furthermore, most oncologists surveyed considered 3 months to be a suitable level of additional benefit for the addition of SBRT (experimental treatment) to be considered a worthwhile intervention. Therefore median PFS for the SBRT group is assumed to be 6 months. Using these estimates together with a significance level of 5% (two-sided), 90% power, a 2:1 allocation ration (SBRT treatment:control), 110 randomised patients (anticipated 73:37) in total is required to obtain 97 PFS events. The sample size calculation uses the log rank test due to the possibility of non-proportional hazards.

The sample size calculation assumes a recruitment period of 36 months with a 6 monthly accrual percentage of total of 5%: 10%: 15%: 20%: 25%: 25% with a minimum of 6 months follow-up (total duration 42 months). It is assumed that the lost to follow up rate will be <1% due to the frequency of follow-ups in line with routine practice and the short expected median time to reaching the primary endpoint.

It is estimated that up to 20% of patients will be registered and found not to be eligible. In order for 110 patients to be randomised it is estimated that 138 patients will need to be registered. Data to base these estimates on is limited and therefore the Independent Data Monitoring Committee (IDMC) and Trial Management Group (TMG) will review the number of patients registered during the trial.

Phase III trial: an average median overall survival of 12 months (mutation types combined) in the control group is anticipated at this stage. The number of patients required for the phase III trial will be influenced considerably by the designated magnitude of minimum clinically important difference and this estimate will be refined after the phase II trial. Using the log rank method as above and assuming a 5-year recruitment period, a total of 272-875 patients (power 80%, alpha 5%) would be required to detect a 6 month or 3 month improvement in overall survival with SBRT (12 to 18 month and 12 to 15 month improvement respectively) and it is anticipated that the designated number of patients

required will lie within this range. It is envisaged that patients recruited to the phase II component will also contribute to the phase III endpoint given the rare population and the integrated design. Assumptions made about the phase III trial design and sample size will be re-assessed for relevance and suitability during the transition phase (Appendix 1). Should the target sample size for phase III be at the lower end of the range recruitment is likely to be completed more quickly.

13.2 Treatment Allocation

Treatment allocation is by minimisation with a random element; balancing factors will be mutation type (e.g. EGFR or other actionable mutation), tumour burden (high vs. low) and treating centre. The virtual MDT will access the scan first used to diagnose metastatic disease and the diagnostic CT scan in order to determine if the patient was allocated to the SBRT arm, would SBRT be performed on *all* known disease. If yes this would indicate low tumour burden, if no high tumour burden. The virtual MDT will inform sites whether the patient has high or low tumour burden.

13.3 Statistical Analysis Plan

Analyses of efficacy will be according to the intention to treat principle. Time to event endpoints will be presented using Kaplan Meier survival plots and compared between treatment groups using the log-rank test. Hazard ratios will be derived from Cox proportional hazards models or methods such as restricted mean survival should the assumption of proportionality not be met. A planned subgroup analysis will explore treatment effect by mutation status (e.g. EGFR+ vs. other mutation), however it is recognised there is limited power to estimate these subgroup effects and thus analyses will be interpreted with the appropriate caution.

Patterns of further disease progression will be summarised by treatment group to document the natural history of oncogene-addicted lung disease.

Acute and late toxicity related to SBRT treatment, both physician and patient reported, will be analysed separately and summarised as frequencies and percentages at each time point with adjustment made for multiple testing. The proportion experiencing toxicity of any grade and grade \geq 3 will be presented and any comparisons made between randomised treatment groups using Fisher's exact tests. All safety analyses will use a safety population which will be pre-defined in the Statistical Analysis Plan.

Quality of life (QoL) data will be analysed using standard algorithms to derive scores and handle missing data according to the chosen questionnaire's scoring manual. Descriptive statistics (median, IQR, range) will be presented by treatment group at each timepoint. Analyses to account for the longitudinal nature of the data may also be used.

The integral translational work will include assessment of ctDNA clearance as a binary outcome with comparison between randomised treatment groups made using Fisher's exact tests. Logistic regression models will be used to adjust for any relevant baseline characteristics. Exploratory analyses

will look at the genetic relationship between baseline circulating biomarkers and archival tumour samples.

Further details of analysis methods will be specified in a Statistical Analysis Plan in accordance with ICR-CTSU Standard Operating Procedures.

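### The primary PFS test and hazard ratio in section 13.3 name no strata or covariates although allocation is minimised on mutation type and tumour burden: valid, but short of power if both factors are materially prognostic

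*Protocol*

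**What the plan says.** Protocol section 13.2 allocates by minimisation with a random element; the "balancing factors will be mutation type (e.g. EGFR or other actionable mutation), tumour burden (high vs. low) and treating centre". Section 6.1.1 explains that tumour burden is requested at randomisation to limit bias from an uneven split between the groups. Section 9 lists both mutation class and tumour burden among the data required at randomisation.

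Section 13.3 gives the efficacy analysis: "Time to event endpoints will be presented using Kaplan Meier survival plots and compared between treatment groups using the log-rank test". Hazard ratios come from Cox models, or methods such as restricted mean survival are used if proportionality fails. No stratum or covariate is named for PFS. In the same section, mutation status appears only as a planned subgroup, and adjustment for baseline characteristics is written in only for ctDNA clearance. Further analysis detail is left to an SAP.

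Section 13.1 sizes the trial on the log-rank test, again with no strata: "110 randomised patients (anticipated 73:37) in total is required to obtain 97 PFS events". Section 13.4 calls SBRT futile if the hazard ratio exceeds 1.0 at 49 PFS events, without saying which model supplies that ratio.

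**The concern.** Minimising on a factor makes sense mainly if it is thought to affect outcome. Minimisation removes most between-arm variation in that factor, but a plain log-rank variance still allows for it. When the factor matters, the test statistic is therefore less variable than the test assumes, and the test rejects too rarely under the null. Separately, leaving a prognostic factor out of a proportional hazards analysis pulls the marginal hazard ratio towards 1 and costs power.

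The design has no reserve to absorb this: it is sized for 90% power at exactly 97 events. The futility rule also turns on a point estimate, which differs between an adjusted and an unadjusted model.

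**Working it through.** **Inputs from the protocol (13.1, 13.2).** Two-sided alpha 5%, power 90%, 2:1 allocation, 110 patients (73:37), 97 events. Control median PFS is 3 months, from a clinician survey; "median PFS for the SBRT group is assumed to be 6 months". Under exponential PFS the hazard ratio is 3/6 = 0.5. Accrual lasts 36 months at 5, 10, 15, 20, 25 and 25% per six months, with analysis at 42 months.

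**Step 1: the plan's own figure.** Schoenfeld: D = (z₀.₉₇₅ + z₀.₉₀)² / [p(1−p)(ln HR)²].
- With p = 1/3: (1.960 + 1.282)² / (0.2222 × 0.4805) = 10.51 / 0.1068 = 98.4, so 99 events.
- With p = 37/110: 98 events.
- Power at the stated 97 events: 89.6 to 89.7%.
- Expected events at 42 months: 37 × 0.9557 + 73 × 0.8371 = 35.4 + 61.1 = 96.5.

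The stated 97 events and 90% power hold.

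**Step 2: plain against four-stratum log-rank.** Simulation of 12,000 trials per cell, with 2:1 minimisation on both factors and 20 centres, and the protocol's accrual. Assumptions, because the documents give none: 70% of patients in one mutation class, 50% high burden, the same prognostic hazard ratio for both factors, centre not prognostic, and 80% preference in the minimisation. PFS is exponential within each factor combination, with treatment hazard ratio 0.5 and the overall control median set to 3 months. Halving every hazard doubles every time, so S_SBRT(t) = S_control(t/2) and the overall SBRT median is 6 months. The protocol's medians are therefore met in every row.

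| Prognostic HR, each factor | Power, plain | Power, 4 strata | Type I, plain | Type I, 4 strata |
|---|---|---|---|---|
| 1.0 | 90.1% | 88.2% | 5.4% | 5.3% |
| 1.25 | 89.1% | 87.5% | 4.6% | 4.7% |
| 1.5 | 87.3% | 87.8% | 5.0% | 5.3% |
| 1.75 | 85.0% | 87.8% | 4.3% | 5.5% |
| 2.0 | 81.8% | 87.5% | 3.8% | 5.2% |
| 2.5 | 74.7% | 86.1% | 2.7% | 4.9% |

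Monte Carlo standard error is about 0.2 points for type I error and 0.3 to 0.4 for power. The plain test loses power from about 1.5 and is clearly conservative from about 1.75 to 2.0. The four-stratum test costs about 2 points (90.1 − 88.2 = 1.9) when the factors are inert.

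**Step 3: both factors as Cox covariates.** Simulation of 3,000 trials per cell, with the same accrual, cut-off and prevalences, and minimisation on the two factors (standard error 0.5 to 0.8 points for power).

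| Prognostic HR, each factor | Power, unadjusted | Power, Cox with both factors |
|---|---|---|
| 1.0 | 88.9% | 89.1% |
| 1.5 | 86.4% | 89.7% |
| 2.0 | 81.8% | 89.3% |
| 2.5 | 75.4% | 88.5% |

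Adjusted type I error was 4.9 to 5.5%. A further run of 1,500 trials per cell gave, for plain / four strata / Cox with covariates, 91/88/91% at 1.0, 87/86/89% at 1.5, 82/88/90% at 2.0 and 76/87/90% at 2.5. The two runs agree within simulation error.

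**Step 4: the futility rule.** In the 3,000-trial simulation with no true effect, adjusted and unadjusted hazard ratios fell on opposite sides of 1.0 in 10%, 14% and 16% of trials at prognostic hazard ratios of 1.5, 2.0 and 2.5.

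**Step 5: centre.** Section 5.2 expects about 20 UK sites plus EORTC sites. Even 20 sites give 110/20 = 5.5 patients each, and crossing them with four strata gives 80 cells for 110 patients. Stratifying by centre is not workable.

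**The case against.** The strongest reply is that the protocol never calls the PFS analysis unstratified or unadjusted. It names a test and a model family and leaves further detail to an SAP, which could add strata or covariates without contradicting 13.3. This stands. A reader might infer that the protocol commits the trial to an analysis that ignores its balancing factors; that would be reading a commitment into silence. What remains is that 13.3 does name a method for the primary comparison, and writes in adjustment for another outcome but not for this one.

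Second, the harm is conditional. At a prognostic hazard ratio of 1.25 or less the plain test is not harmed. The only figures by mutation are in section 1.2: median PFS on TKI of 8 to 10 months (ALK) and 9 to 13 months (EGFR), midpoints 9 and 11, ratio 11/9 = 1.2. They describe an earlier point in the disease than oligoprogression and are only indicative. With mutation at 1.2 and burden at 2.0, a simulation of 4,000 trials per cell gave 85.2% plain against 86.5% with four strata, and plain null rejection of 4.6%. The larger losses need both factors to be strong. This also stands.

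Third, four-stratum stratification does not restore 90%: it reaches 86 to 88% in every row of step 2. That is true of the stratified log-rank but not of covariate adjustment (step 3).

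Fourth, no operating characteristics are available for the futility rule under an adjusted model. Step 4 therefore shows only that the model must be named, not which one performs better.

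**Conclusion.** The point holds as a conditional matter of efficiency and clarity. If 13.3 is followed as written, and mutation type and tumour burden each carry a prognostic hazard ratio of about 1.5, 2.0 or 2.5, power is about 87%, 82% or 75% against the planned 90%. At 2.0 and 2.5 the type I error falls to about 3.8% and 2.7%. These figures rest on assumed prognostic strengths and prevalences; the documents give neither. Adjusting for the two factors holds about 89 to 90% throughout, with no measurable cost if they are inert.

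Three stronger conclusions might be drawn, and none is supported. The sample size is not wrong: 97 events, 110 patients and 90% power reproduce. A positive result would not be unsafe: the plain test errs towards caution. The unadjusted hazard ratio is not biased: it is a marginal quantity, which lies nearer to 1 than the within-stratum one because the hazard ratio is non-collapsible.

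**What to change.** In section 13.3, or by confirming it in the SAP before unblinded data are seen:

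- Base the primary PFS test and hazard ratio on a Cox model with treatment, mutation type (EGFR vs other) and tumour burden (high vs low) as covariates, and name the test statistic.
- Prefer this to a four-stratum log-rank, which costs about 2 points of power if the factors are not prognostic.
- Leave centre out of the primary model.
- Report the plain log-rank as supportive. The protocol chose it because of possible non-proportional hazards ("The sample size calculation uses the log rank test due to the possibility of non-proportional hazards"), so keep the restricted-mean fallback.
- In section 13.4 and Appendix A1, state in advance which model gives the hazard ratio for the 49-event futility rule.

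The cost is wording only. Both factors are already collected at randomisation, and sample size and event target are unchanged. If the SAP already says this, one confirming sentence closes the point.
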